5.3 Study Procedures

5.3.1 Screening Evaluations

The following procedures must occur during screening:

1. Complete history and physical including assessment of ECOG performance status, weight, and digital rectal exam within 60 days prior to registration (Appendix A).

Version 09/11/2025 page 25 of 63

^{** &}quot;point" defined as 0.035cc or less

- 2. CBC with differential and complete metabolic panel within 60 days prior to registration.
- 3. Urine or serum pregnancy test for female patients that are of childbearing potential within 14 days prior to registration.
- 4. CT chest/abdomen/pelvis or staging within 60 days prior to registration. If PET/CT scan is done, then CT chest/abdomen/pelvis not required.
- 5. MRI of the pelvis within 60 days prior to registration.
- 6. Endoscopy with colonoscopy, sigmoidoscopy, or endoscopy of the locoregionally recurrent tumor within 60 days of registration (recommended if feasible)
- 7. OPTIONAL biopsy at time of SOC endoscopy.
- 8. Charlson Comorbidity Index score will be calculated based on patient comorbidities and age.

5.3.2 Pre-RT Evaluations

No more than 30 days before the start of radiation treatment, the following procedures must occur:

- 3. CBC with differential and CMP
- 4. Study labs (CEA, SCCA, CRP, LDH)
- 5. QOL questionnaires (Appendices B, C)
- 6. Assessment of baseline symptoms

5.3.3 On Therapy Evaluations

The following evaluations will occur while the patient is receiving radiation therapy:

- One on-treatment visit during the 5 fractions of RT including a physical exam, vital signs, assessment of ECOG performance status, and digital rectal exam.
- Physician-reported assessment of patient symptoms will be done using CTCAE version 5.0 once during radiation therapy (preferably during fraction 4 or 5).

5.3.4 Post-Radiation Evaluations

All patients will be followed from time of enrollment until 1 year post radiation Mandatory follow-up time points are as below. In the event that an in-person evaluation is not possible, or if not indicated by the treating investigator, a telehealth visit may be performed in its place.

- 1-2 weeks post-RT
- 6-8 weeks post-RT
- 3 months post-RT (+-/- 2 weeks)
- 6 months post-RT (+/- 2 weeks)
- 9 months post-RT (+/- 2 weeks)
- 12 months post-RT (+/- 2 weeks)

Version 09/11/2025 page 26 of 63

5.3.4.1 Treatment Response Assessment

The following assessments should be performed 6 weeks to 3 months after radiation (but should be completed before surgery if the patient will be undergoing salvage surgery) and again 6 months after radiation:

- MRI pelvis
- CT chest/abdomen with contrast (if a PET is performed, a CT is not required)
- CBC with differential and CMP
- Study labs (CEA, SCCA, CRP, LDH)

In addition, MRI pelvis and CT chest/abdomen with contrast should be performed at 9 and 12 months after radiation. Endoscopies are optional after radiation therapy.

5.3.4.2 Adverse Events and PRO QOL

Patients will be clinically evaluated after completion of radiation therapy at the time points listed above. Physician reported assessment of patient symptoms will be done using the NCI-CTCAE v5.0 at each time point. Patient evaluation by a physician should occur sooner for any symptoms concerning for treatment-related toxicity or disease recurrence/progression. PROs will be assessed at all time points (except the 6-8 weeks post-RT time point) using the QOL questionnaires (Appendices B, C).

5.4 Definitions of Evaluability

Endpoint	In order to be evaluable for this endpoint, a		
	patient must		
	Have received at least one fraction of study		
	radiation. Patients will be evaluated for DLTs		
Maximum tolerated dose	from the start of treatment through 6 months		
	after the start of treatment. DLT is defined in		
	Section 5.2.1.		
Clinical complete response rate.	Have received at least one fraction of study		
	radiation and undergone response assessment by		
	DRE, endoscopy, and/or cross-sectional		
	imaging.		
Freedom from locoregional	Have received at least one fraction of study		
progression (FFLP) at 12 months.	radiation and undergone response assessment.		
Overall survival at 12 months.	Have received at least one fraction of study		
	radiation		
Progression-free survival at 12	Have received at least one fraction of study		
months.	radiation and undergone response assessment.		

Version 09/11/2025 page 27 of 63

Patient reported quality of life.	Have completed the EORTC QLQ-C30 and/or QLQ-CR29 QOLs at pre-treatment and a minimum of one post-treatment time point
Toxicity	Have received at least one fraction of study radiation. Patients are evaluated from first receiving study radiation until 12 months after the conclusion of radiation.
Association of pre-treatment SCCA and post-treatment SCCA with PFS and OS at 6 months.	Have had blood drawn for SCCA at screening and after completion of study radiation
Levels of serum inflammatory markers.	Have had blood drawn for CRP and LDH after completion of study radiation

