3	5	8	40	72.00	60.00

Note – the first 6 evaluable patients enrolled will be treated at Dose Level 1 Please refer to section 10.0

Version 09/11/2025 page 10 of 63

SCHEDULE OF ACTIVITIES

	Screening	Pre- treatment ⁸	Radiation	1-2 Weeks post RT	6-8 Weeks post RT	3 Mo post RT ¹	6 Mo post RT ¹	9 Mo post RT ¹	12 Mo post RT ¹	
Informed consent	X^2									
H&P / PS / weight / DRE ¹³	X^2		X^3	X	X	X	X	X	X	
MRI pelvis ⁴	X^2				X	5	X	X	X	
CT chest / abdomen / pelvis with contrast ⁶	X^2				X ⁶		X	X	X	
Endoscopy ⁷	X^2				X	15				
OPTIONAL biopsy	$X^{2, 15}$				Х	ζ				
CBC w/diff	X^2	X^2			X^9		X			
CMP	X^2	\mathbf{X}^2			X^9		X			
CEA		X			X^9		X			
SCCA		X			X ⁹		X			
CRP		X			X ⁹		X			
LDH		X			X ⁹		X			
Pregnancy test	$X^{10,11}$									
Radiation therapy			X^{12}							
EORTC QLQ-C30		X		X		X	X	X	X	
EORTC QLQ-C29		X		X		X	X	X	X	
Adverse events		X	X^3	X	X	X	X	X	X	

- 1. +/- 2 weeks
- 2. No more than 60 days prior to registration. Screening and baseline labs can be the same draw provided the timing aligns.
- 3. Performed once during radiation therapy.
- 4. Cross-sectional imaging with either MRI or CT is acceptable.
- 5. MRI pelvis and CT chest/abdomen with contrast may be obtained 6 weeks to 3 months after radiation completion with a RECIST read at 3 months only.
- 6. If PET/CT scan is done, then CT chest/abdomen/pelvis not required.
- 7. Endoscopy with colonoscopy, sigmoidoscopy, or proctoscopy will be performed if feasible after screening.
- 8. Baseline labs and QOL assessments should be performed within 30 days of radiation therapy.
- 9. Labs should be drawn once 6 weeks to 3 months after radiation completion but should be drawn before surgery if the patient undergoes salvage surgery.
- 10. Mandatory for women of childbearing potential.
- 11. Within 14 days of registration.
- 12. 5 fractions over 1 week.
- 13. DRE only to be done if feasible.15. OPTIONAL endoscopy with biopsy performed 6 weeks to 3 months after completion of RT; for research purposes only.
- 15. OPTIONAL screening biopsy to be performed at time of baseline SOC endoscopy.

Version 09/11/2025 page 11 of 63

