5.8 Duration of Follow-up

Patients will be followed for 12 months following the completion of IMPT or until death, whichever occurs first. Patients removed from study for unacceptable adverse events will be followed until resolution or stabilization of the adverse event. Follow-up is described in Section 5.3.4. Patients will be followed by office visits, phone calls, and review of medical record. Any additional follow-up and imaging will be obtained off-study as per routine clinical policies of the treating physician.

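### The exploratory SCCA endpoint is worded for PFS and OS at 6 months, although both are collected to 12 months and section 10.2.5 sets no 6-month cut; a sample drawn at 6 months cannot be prognostic for that horizon

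*Combined protocol and SAP*

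**What the plan says.** Section 5.4 lists the endpoint as "Association of pre-treatment SCCA and post-treatment SCCA with PFS and OS at 6 months", and the protocol summary and section 2 give the same horizon. None of the three gives a reason for it.

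The rest of the plan works to 12 months:

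- Section 5.8: "Patients will be followed for 12 months following the completion of IMPT or until death, whichever occurs first".
- Section 5.3.4.1: "MRI pelvis and CT chest/abdomen with contrast should be performed at 9 and 12 months after radiation", so later progressions are looked for.
- Section 5.4 has "Overall survival at 12 months" as a secondary endpoint, with PFS and FFLP at the same horizon.

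SCCA is measured before treatment and twice afterwards. Footnote 9 of the Schedule of Activities says "Labs should be drawn once 6 weeks to 3 months after radiation completion", and section 5.3.4.1 asks for the study labs, which include SCCA, "and again 6 months after radiation". Section 5.3.4 gives the 6-month visit a window of two weeks either side. The evaluability row for SCCA requires a draw after radiation but does not say which one.

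Section 10.2.5 does not name SCCA. Its general rule counts survival from the end of radiation, censors event-free patients at last follow-up, and relates explanatory variables to survival times with a Cox model.

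**The concern.** The objective is the prognostic value of SCCA. In a trial of 20 patients the information for that is the number of events that follow the marker measurement. The endpoint wording stops the clock halfway through follow-up that the trial completes anyway.

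The timing of the samples adds a second difficulty. A marker can only be prognostic for events after it is measured. The 6-month draw coincides with the 6-month horizon and with the 6-month scans, so progression seen then is concurrent with the marker. The plan neither excludes this draw nor says how either post-treatment draw is to be related to outcomes counted from the end of radiation.

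At stake are precision in an exploratory analysis and a clear instruction to the analyst, who has one text that says 6 months and another that implies all available follow-up.

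**Working it through.** The plan gives no event count, effect size or power for the SCCA analysis, so there is no figure of its own to reproduce. The check asks how many events the 6-month wording would set aside.

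**Inputs.** N = 20 (section 10.2). Three-year OS of 24% after reirradiation alone and one-year OS of 86% after reirradiation with surgery (literature cited in section 1.2). No PFS rate is given, so median PFS is assumed at 3, 6 and 12 months. All 20 patients are taken as evaluable and fully followed; losses would lower every count.

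**Formula.** Constant hazard: S(t) = s0^(t/t0), where s0 is the survival at the known time t0. Expected events by t are 20 × (1 − S(t)). The share of 12-month events falling after month 6 is (S(6) − S(12)) / (1 − S(12)).

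For reirradiation alone, S(12) = 0.24^(12/36) = 0.621 and S(6) = 0.24^(6/36) = 0.788. Deaths are 20 × 0.212 = 4.2 by 6 months and 20 × 0.379 = 7.6 by 12.

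| Basis | S(6) | S(12) | Events by 6 mo | Events by 12 mo | Share after 6 mo |
|---|---|---|---|---|---|
| OS, reirradiation alone | 0.788 | 0.621 | 4.2 | 7.6 | 44% |
| OS, reirradiation with surgery | 0.927 | 0.860 | 1.5 | 2.8 | 48% |
| PFS, assumed median 3 mo | 0.250 | 0.0625 | 15.0 | 18.8 | 20% |
| PFS, assumed median 6 mo | 0.500 | 0.250 | 10.0 | 15.0 | 33% |
| PFS, assumed median 12 mo | 0.707 | 0.500 | 5.9 | 10.0 | 41% |

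**Sensitivity to the hazard shape.** With S(t) = exp(−λt^k) passing through the same OS figures, the share of deaths after month 6 is 31% and 37% at k = 0.7 (early hazard) and 55% and 58% at k = 1.3 (rising hazard). For PFS with medians of 3 to 12 months, the same range of k gives 17% to 51%.

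**Outcome time left after each post-treatment sample.**

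- Draw at 6 weeks to 3 months: 6 − 1.5 = 4.5 down to 6 − 3 = 3 months before the 6-month horizon. After a draw at 3 months, expected deaths are 20 × (S(3) − S(6)) = 2.0 or 0.7 to month 6, and 20 × (S(3) − S(12)) = 5.3 or 2.1 to month 12.
- Draw at 6 months: none, or about two weeks if taken at the start of the visit window. With a 12-month horizon, 20 × (S(6) − S(12)) = 3.3 or 1.3 later deaths, and 3.8, 5.0 or 4.1 later PFS events for the three assumed medians.

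**Events before the draw.** Section 10.2.5 counts from the end of radiation. Before a draw at 3 months, 20 × (1 − 0.888) = 2.2 or 20 × (1 − 0.963) = 0.7 deaths are expected. A sample value cannot be set against time or events that precede it without immortal-time bias.

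**What the longer horizon buys.** Assume a median split of SCCA, a hazard ratio of 3 and two-sided alpha of 0.05. Schoenfeld's formula, power = Φ(ln 3 × √(events/4) − 1.96), gives 20% with 4.2 events and 33% with 7.6; it gives 41% with 10 and 57% with 15. For 80% power, 4 × (1.96 + 0.84)² / (ln 3)² comes to 27 events after rounding up.

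**The case against.** The strongest reply is that nothing need be lost. The only analysis text, section 10.2.5, censors at last follow-up and uses a Cox model; applied to SCCA it would use all 12 months. The protocol is also loose with its horizons: PFS and FFLP are defined as times to event yet carry a 12-month label, while their objectives ask for medians. On that view the 6-month label is a slip, and the data to month 12 are collected either way. This stands in part: the loss arises only if the endpoint wording is followed. But section 10.2.5 never mentions SCCA, and the 6-month horizon appears in three places, so the label cannot simply be read away.

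A second reply is that the plan never commits to using the 6-month draw as a predictor. That is correct, and the earlier draw satisfies the evaluability rule. The gap is that the choice is left open.

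A reader might also infer that the plan is certain to discard a third to a half of the events. The documents do not support that as a fact. They give no PFS rate, and the 62% for 12-month OS is a back-calculation from a three-year figure. Under a constant hazard the share falls below a third when 12-month event-free survival is under 25%, and under a rising hazard it can exceed a half.

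**Conclusion.** The point holds as a minor, costless improvement. The 6-month wording conflicts with the general survival rule and gives up follow-up that the trial already obtains. If applied, it sets aside 44% to 48% of the 12-month deaths under a constant hazard at the OS rates in section 1.2 (31% to 58% over the Weibull shapes examined), and about 20% to 41% of PFS events at assumed medians of 3 to 12 months. A sample drawn at 6 months cannot be prognostic for a 6-month horizon.

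Two stronger readings should be resisted. One is that the endpoint as worded leaves nothing to predict. That is true only of the 6-month sample: pre-treatment SCCA has the full 6 months, and the earlier post-treatment sample has 3 to 4.5. The other is that the short horizon is what makes the objective unattainable. With 20 patients, events are too few for a firm answer at 12 months as well. The endpoint is exploratory, no decision hangs on it, and it stays descriptive on either horizon.

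**What to change.** - In the protocol summary, section 2 and section 5.4, define the endpoint as the association of SCCA with PFS and OS as time-to-event outcomes over the full 12 months of follow-up.
- Name this analysis in section 10.2.5, so that the endpoint and the censoring rule agree.
- Relate pre-treatment SCCA to all events from the end of radiation. The evaluability row now asks for both a baseline and a post-radiation draw; for this part it should require the baseline draw only, so that early deaths are not excluded.
- Relate each post-treatment sample (6 weeks to 3 months, and 6 months) only to events after its draw, by a landmark at the draw or as a time-dependent covariate, and state which draw each analysis uses.
- Report the results as descriptive, with event counts and confidence intervals.

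The cost is wording in four places. No visit, blood draw or scan is added, and the analysis waits only for 12-month follow-up that the trial completes anyway.

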5.5 Supportive Care Guidelines

Standard antiemetics, anti-diarrheals, and pain medications may be provided at the discretion of the treating radiation oncologist(s) and physicians who evaluate the patients for follow up. Grade 3-5 adverse events may require hospitalization and inpatient management.

5.6 Women of Childbearing Potential

Women of childbearing potential (defined as women with regular menses, women with amenorrhea, women with irregular cycles, women using a contraceptive method that precludes withdrawal bleeding, and women who have had a tubal ligation) are required to have a negative urine or serum pregnancy test within 14 days prior to the first fraction of radiation therapy.

Female and male patients (along with their female partners) are required to use two forms of acceptable contraception, including one barrier method, during participation in the study and 30 days following the fraction of radiation therapy.

If a patient is suspected to be pregnant, radiation therapy should be immediately discontinued. In addition, a positive urine test must be confirmed by a serum pregnancy test. If it is confirmed that the patient is not pregnant, the patient may resume dosing.

If a female patient or female partner of a male patient becomes pregnant during therapy or within 30 days after the last fraction of radiation, the investigator must be notified in order to facilitate outcome follow-up.

5.7 **Duration of Therapy**

If at any time the constraints of this protocol are considered to be detrimental to the patient's health and/or the patient no longer wishes to continue protocol therapy, the protocol therapy should be discontinued and the reason(s) for discontinuation documented in the case report forms.

Version 09/11/2025 page 28 of 63

In the absence of treatment delays due to adverse events, treatment may continue for 5 fractions or until one of the following criteria applies:

- Documented and confirmed disease progression
- Death
- Adverse event(s) that, in the judgment of the investigator, may cause severe or permanent harm or which rule out continuation of study drug
- General or specific changes in the patient's condition render the patient unable to receive further treatment in the judgment of the investigator
- Suspected pregnancy
- Serious noncompliance with the study protocol
- Lost to follow-up
- Patient withdraws consent
- Investigator removes the patient from study
- The Siteman Cancer Center decides to close the study

Patients who prematurely discontinue treatment for any reason will still be followed as indicated in the study calendar.

5.8 Duration of Follow-up

Patients will be followed for 12 months following the completion of IMPT or until death, whichever occurs first. Patients removed from study for unacceptable adverse events will be followed until resolution or stabilization of the adverse event. Follow-up is described in Section 5.3.4. Patients will be followed by office visits, phone calls, and review of medical record. Any additional follow-up and imaging will be obtained off-study as per routine clinical policies of the treating physician.

5.9 Lost to Follow-Up

A participant will be considered lost to follow-up if he or she fails to return for 3 scheduled visits and is unable to be contacted by the study team.

The following actions must be taken if the participant fails to return to clinic for a required study visit:

- The study team will attempt to contact the participant and reschedule the missed visit within 5 business days and counsel the participant on the importance of maintaining the assigned visit schedule and ascertain if the participant wishes to and/or should continue in the study.
- O Before a participant is deemed lost to follow-up, the investigator or designee will make every effort to regain contact with the participant (where possible, 3 telephone calls and, if necessary, a certified letter to the participant's last known mailing address). These contact attempts should be documented in the participant's medical record or study file.

Version 09/11/2025 page 29 of 63

• Should the participant continue to be unreachable, he or she will be considered to have withdrawn from the study with a primary reason of lost to follow-up.

6 REGULATORY AND REPORTING REQUIREMENTS

The entities providing oversight of safety and compliance with the protocol require reporting as outlined below. Please refer to Appendix D for definitions and Appendix E for a grid of reporting timelines. All investigators treating patients on this study are responsible for ensuring that serious adverse events (as defined in Appendix B) are reported to the Sponsor-Investigator within an adequate timeframe for the event to be assessed by the Sponsor-Investigator for reporting to HRPO, QASMC, and/or FDA. Note that for investigator-initiated studies, the term "Sponsor-Investigator" refers to the investigator holding the IND.

Adverse events will be tracked from start of treatment through 12 months after completion of radiation therapy. All adverse events must be recorded on the toxicity tracking case report form (CRF) with the exception of:

- Baseline adverse events, which shall be recorded on the medical history CRF
- Toxicities that are definitely or highly likely related to salvage surgery and/or salvage chemotherapy

Refer to the data submission schedule in Section 7 for instructions on the collection of AEs in the EDC.

Reporting requirements for Washington University study team may be found in Section 6.1.

6.1 WU PI Reporting Requirements

6.1.1 Reporting to the Human Research Protection Office (HRPO) at Washington University

Reporting will be conducted in accordance with Washington University IRB Policies.

Pre-approval of all protocol exceptions must be obtained prior to implementing the change.

6.1.2 Reporting to the Quality Assurance and Safety Monitoring Committee (QASMC) at Washington University

The PI (or designee) is required to notify the QASMC of any unanticipated problems involving risks to participants or others occurring at WU or any BJH or SLCH institution that has been reported to and acknowledged by HRPO.

Version 09/11/2025 page 30 of 63

(Unanticipated problems reported to HRPO and withdrawn during the review process need not be reported to QASMC.)

QASMC must be notified within **10 days** of receipt of IRB acknowledgment via email to [contact]. Submission to QASMC must include the myIRB form and any supporting documentation sent with the form.

6.2 Exceptions to Expedited Reporting

Events that do not require expedited reporting as described in Section 6.1 include:

- planned hospitalizations
- hospitalizations < 24 hours
- respite care
- events related to disease progression

Events that do not require expedited reporting must still be captured in the EDC.

7 DATA SUBMISSION SCHEDULE

Case report forms with appropriate source documentation will be completed according to the schedule listed in this section.

Case Report Form	Submission Schedule
On-Study Form Medical History Form	Prior to starting treatment
Treatment Summary Form	End of treatment
DLT Form	6 months post-treatment
PRO Form	Prior to starting treatment, 1-2 weeks post-treatment, 3 months post-treatment, 6 months post-treatment, 9 months post-treatment, 12 months post-treatment
Toxicity Form	Continuous
Follow Up Form	1-2 weeks post-treatment, 6-8 weeks post-treatment, 3 months post-treatment, 6 months post-treatment, 9 months post-treatment, 12 months post-treatment
Tumor Measurement Form	Baseline, 6-8 weeks post-treatment OR 3 months post-treatment
Progression Form	Time of disease progression
Death Form	Time of death
MedWatch Form	See Section 6.0 for reporting requirements

